Appendix 4. Definitions

Definition of stratification variables

Site: all participating intensive care units (ICUs) will be assigned a number identifying the department.

Haematological malignancy includes any of the following:

- leukemia: Acute lymphoblastic leukemia (ALL), acute myelogenous leukemia (AML), chronic myelogenous leukemia (CML), chronic lymphocytic leukemia (CLL).
- lymphoma: Hodgkin's disease, Non-Hodgkin lymphoma (e.g. small lymphocytic lymphoma (SLL), diffuse large B-cell lymphoma (DLBCL), follicular lymphoma (FL), mantle cell lymphoma (MCL), hairy cell leukemia (HCL), marginal zone lymphoma (MZL), Burkitt's lymphoma (BL), post-transplant lymphoproliferative disorder (PTLD), T-cell prolymphocytic leukemia (T-PLL), B-cell prolymphocytic leukemia (B-PLL), Waldenström's macroglobulinemia, other NK- or T-cell lymphomas
- Multiple myeloma/plasma cell myeloma

Definition of inclusion criteria

Acute admission to the ICU: a non-planned admission. It does not include planned recovery after surgery or similar planned admissions. ICU admission does not include admissions to semi intensive care, intermediate intensive care or similar beds.

Age: the age of the patient in whole years at the time of randomisation. The age will be calculated from date of birth

Shock: at least one of the following:

- systolic pressure < 90 mmHg
- mean arterial pressure < 70 mmHg
- use of vasopressors or inotropes (norepinephrine, epinephrine, phenylephrine, vasopressin or dopamine, dobutamine, milirinone or levosimendan)
- lactate > 4 mmol/l

Renal replacement therapy: acute or chronic intermittent or continuous renal replacement therapy

Patients with expected duration of invasive mechanically ventilation > 24 hours: the treating clinician estimates that the patient will be invasively mechanically ventilated for more than 24 hours. When in doubt of this forecast the patient should be enrolled

Coagulopathy: platelets < 50 x 10⁹/l or international normalized ratio (INR) > 1.5 or prothrombin time (PT) > 20 seconds documented within the last 24 hours

Treatment with anticoagulant drugs: ongoing treatment with: Dipyridamole, vitamin K antagonists, ADP-receptor inhibitors, therapeutic doses of low molecular weight heparin, new oral anticoagulant drugs, intravenous direct thrombin (II) inhibitors and similar drugs. Acetylsalicylic acid (all doses) and low molecular weight heparin in prophylactic doses are NOT included

History of coagulopathy: coagulopathy defined as platelets < 50 x 10⁹/l AND/OR INR > 1.5 AND/OR PT > 20 seconds within 6 months prior to hospital admission.

History of chronic liver disease: portal hypertension, cirrhosis proven by biopsy, computed tomography (CT) scan or ultrasound, history of variceal bleeding or hepatic encephalopathy in the past medical history

Definition of exclusion criteria

Contraindications to proton pump inhibitors (PPI): any history of intolerance to PPI or additives or treatment with atazanavir (HIV medication)

Ongoing treatment with PPI and/or histamine-2-receptor antagonists (H2RA): ongoing is defined as treatment not being discontinued at ICU admission. If clinicians do not find indication for continuation of treatment with PPI/H2RA during ICU stay, the patient will be eligible for inclusion.

GI bleeding during current hospital admission: GI bleeding of any origin (both upper and lower) documented in the patient charts

Peptic ulcer: peptic ulcer confirmed by endoscopy or other method during current hospital admission

Organ transplant: any kind of organ transplant during current hospital admission.

Withdrawal from active therapy or brain death: patients where withdrawal or brain death is documented in the patient charts

Known pregnancy: fertile woman with positive urine human chorionic gonadotropin (hCG) or plasma-hCG

Consent not obtainable according to national regulations: patients where the clinician or investigator is unable to obtain necessary consent before inclusion of the patient according to the national regulations

Definition of baseline variables

Sex: the genotypic sex of the patient

Age: defined in inclusion criteria

Date of admission to hospital: the date of admission to the first hospital the patient was admitted to during the current hospital admission

Elective surgery: surgery during current hospital admission scheduled 24 hours or latter in advance

Emergency surgery: surgery during current hospital admission that was added to the operating room schedule 24 hours or less prior to surgery

Medical admission: when no surgery has been performed during current hospital admission OR surgery has been performed more than 1 week prior to ICU admission

Treatment with anticoagulants at hospital admission and at ICU admission: anticoagulants are defined in inclusion criteria

Treatment with non-steroidal anti-inflammatory drugs (NSAID) and acetylsalicylic acid at hospital admission: treatment with all doses of these drugs at hospital admission

Treatment with intravenous thrombolysis: treatment with all kinds of intravenous thrombolysis within 3 days prior to randomisation

Coagulopathy: defined in inclusion criteria

Treatment of suspected or confirmed *Clostridium difficile* infection (CDI) during current hospital admission

Coexisting illness must have been present in the past medical history prior to ICU admission and are defined as follows:

- Chronic lung disease: chronic obstructive pulmonary disease (COPD), asthma or other chronic lung disease or treatment with any relevant drug indicating this at admission to hospital
- Previous myocardial infarction: history of myocardial infarction
- Chronic heart failure: New York Heart Association Functional Class (NYHA) III-IV. NYHA III: The patient has marked limitations in physical activity due to symptoms (fatigue, palpitation or dyspnoea) even during less than ordinary activity (walking short distances 20-100 m. or walking up stairs to 1st floor). The patient is only comfortable at rest. NYHA class 4: The patient is not able to carry out any physical activity (without discomfort (fatigue, palpitation or dyspnoea). Symptoms are present even at rest and the patient is mostly bedbound
- History of chronic renal failure: need of any form of chronic renal replacement therapy within the last year
- Liver disease: defined in baseline variables
- History of coagulopathy: defined in baseline variables
- Immunosuppression: patients treated with at least 0,3 mg/kg/day of prednisolone equivalent for at least 1 month in the 6 months prior to ICU admission
- Metastatic cancer: proven metastasis by surgery, CT scan or any other method
- Hematologic malignancy: defined as stratification variable
- AIDS: HIV positive patients with one or more HIV defining diseases such as pneumocystis jirovecii pneumonia, Kaposi's sarcoma, Lymphoma, tuberculosis or toxoplasma infection

The Simplified Acute Physiology Score (SAPS II) [74] (*appendix 9*) is based on the most extreme (highest or lowest) values from 24 hours prior to randomisation. The score consists of 17 variables: 12 physiologic variables, age, type of admission and 3 variables related to underlying disease to give a total score ranging from 0 to 163, with higher scores indicating greater severity of illness. The score will be calculated from data from the 24 hours prior to randomisation

The Sequential Organ Failure Assessment (SOFA) Score [75] (*appendix 10*) will be calculated from raw physiology and treatment data from the 24 hours prior to randomisation. The SOFA Score consists of weightings for six organ systems to give a total score ranging from 0 to 24, with higher scores indicating a greater degree of organ failure.

Definition of daily collected variables:

Delivery of trial medication: confirmation of administration of the trial drug

Treatment with PPI or H2RA: prescription of any of these drugs in any dose (major protocol violation if the treatment is initiated (e.g. as prophylaxis) without clinical indication (e.g. gastrointestinal bleeding))

Mechanical ventilation: invasive and non-invasive mechanical ventilation including continuous mask CPAP or CPAP via a tracheotomy. Intermittent CPAP is NOT mechanical ventilation.

Circulatory support: continuous infusion of vasopressor or inotrope (norepinephrine, epinephrine, phenylephrine, vasopressin or dopamine, dobutamine, milirinone or levosimendan)

Renal replacement therapy: any form of renal replacement therapy on this day. In patients receiving intermittent renal replacement therapy days between treatments are included

Clinically important GI bleeding, onset of pneumonia, CDI, and acute myocardial ischemia in the ICU are defined as outcomes

Treatment with enteral feeding: any dose of enteral feeding (including oral nutritional intake) during the day

Units of red blood cells: cumulated number of units of red blood cells transfused during the day

Serious adverse reactions (SARs) are defined below

Definition of bleeding variables:

Confirmed diagnosis: diagnosis/origin of bleeding confirmed by endoscopy or other method

Verification of ulcer/gastritis/bleeding oesophageal varices: confirmation of one of the three specific diagnoses by endoscopy or other method

Haemostasis achieved or attempted: documentation in patient charts of haemostasis achieved or attempted by endoscopy, open surgery or coiling

Definitions of outcome measures

Primary outcome:

90-day mortality: death from any cause within 90 days following the day of randomisation

Secondary outcomes:

Proportion of patients with one or more of the following adverse events: clinically important GI bleeding, pneumonia, CDI, and acute myocardial ischemia. The events are defined as follows:

Clinically important GI bleeding: overt GI bleeding* and at least one of the following four features within 24 hours of GI bleeding (in the absence of other causes) in the ICU

- e) spontaneous drop of systolic blood pressure, mean arterial pressure or diastolic blood pressure of 20 mmHg or more
- f) start of vasopressor or a 20% increase in vasopressor dose
- g) decrease in haemoglobin of at least 2 g/dl (1.24 mmol/l)
- h) transfusion of 2 units of packed red blood cells or more

*Overt GI bleeding: hematemesis, coffee ground emesis, melena, haematochezia or bloody nasogastric aspirate

Pneumonia: episodes of newly confirmed pneumonia according to the modified CDC criteria [76]

- Two or more serial chest radiographs with at least one of the following (one radiograph is sufficient for patients with no underlying pulmonary or cardiac disease):
 1. new or progressive and persistent infiltrate
 2. consolidation
 3. cavitation
- AND at least one of the following:
 1. fever (>38°C) with no other recognised cause
 2. leukopenia (white cell count < 4 x 10⁹/l) or leucocytosis (white cell count >12 x 10⁹/l)
- AND at least two of the following

5. new onset of purulent sputum or change in character of sputum, or increased respiratory secretions or increased suctioning requirements
6. new onset or worsening cough, or dyspnoea, or tachypnoea
7. rales or bronchial breath sounds
8. worsening gas exchange (hypoxaemia, increased oxygen requirement, increased ventilator demand)

CDI: Treatment with antibiotics (enteral vancomycin, intravenous or enteral metronidazole, enteral fidaxomicin) for suspected or proven CDI

Acute myocardial ischemia: ST-elevation myocardial infarction, non-ST elevation myocardial infarction or unstable angina pectoris according to the criteria in the clinical setting in question (e.g. elevated biomarkers, ischemic signs on ECG and clinical presentation) AND receiving treatment as a consequence of this (reperfusion strategies (PCI/thrombolysis) or initiation/increased antithrombotic treatment)

Proportions of patients with clinically important GI bleeding: proportion of patients with one or more episodes of clinically important GI bleeding as defined above

Proportion of patients with one or more infectious adverse events: proportion of patients with one or more episodes of pneumonia or CDI

1-year mortality: landmark mortality 1 year post-randomisation

Duration of life support in the ICU: the number of days alive and free from respiratory or circulatory support and of renal replacement therapy as defined below. The outcome will be days alive without use of mechanical ventilation, circulatory support or renal replacement therapy in the 90-day period, and will be defined as the percentage of days without mechanical ventilation, circulatory support and renal replacement therapy (as defined in daily collected variables) in the 90 days after randomisation

Serious adverse reactions: number of serious adverse reactions as defined below

The elements of all composite outcomes will be reported in the supplementary material

A health economic analysis will be performed. The analytic details will be based on the result of the trial and specified (cost-benefit vs cost-minimisation analyses).

Definitions of serious adverse reactions

A serious adverse reaction (SAR) is defined as any adverse reaction that results in death, is life-threatening, requires hospitalization or prolongation of existing hospitalization, or results in persistent or significant disability or incapacity.

Patients will be monitored for onset of SARs occurring between the first dose of trial medication and until discharge from the ICU. If a patient is withdrawn from the trial intervention, SARs will be recorded for 24 hours after the last dose of trial medication or discharge from ICU. If the patient is readmitted to the ICU and trial intervention is reintroduced, data collection for SARs will be resumed. If a patient experiences a SAR the patient will be withdrawn from the trial intervention but data collection and follow-up will be continued (see section 4.3.2)

SARs will be defined as follows:

Anaphylactic reactions defined as urticaria and at least one of the following

- Worsened circulation (>20% decrease in blood pressure or >20% increase in vasopressor dose)
- Increased airway resistance (>20% increase in the peak pressure on the ventilation)
- Clinical stridor or bronchospasm
- Subsequent treatment with bronchodilators

Agranulocytosis is defined as any new, acute and severe drop in granulocytes to $< 0.5 \times 10^9/l$ requiring active monitoring or treatment

Pancytopenia is defined as any new, severe drop in red blood cells, white blood cells and platelets requiring active monitoring or treatment

Acute hepatic failure is defined as severe and progressing hepatic failure as judged by the treating doctor or the investigator

Steven-Johnson syndrome and toxic epidermal necrolysis are defined as severe dermatological reactions with a skin biopsy confirming the diagnosis

Interstitial nephritis is defined as a nephritis affecting the interstitium of the kidneys surrounding the tubules with a kidney biopsy confirming the diagnosis

Angioedema (Quincke's oedema) is defined as a vascular reaction involving the deep dermis, subcutaneous or submucosal tissues, resulting in a characteristic localized oedema.

Adverse reactions not registered will be discussed in *appendix 6*.

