7.2 Secondary outcomes

- Proportion of patients with one or more of the following adverse events: clinically important GI bleeding, pneumonia, CDI, or acute myocardial ischemia in the ICU
- Proportion of patients with clinically important GI bleeding in the ICU
- Proportion of patients with one or more infectious adverse events (pneumonia or CDI) in the ICU
- 1-year “landmark” mortality post-randomisation
- Days alive without the use of mechanical ventilation, renal replacement therapy or circulatory support in the 90-day period
- Number of SARs as defined in *appendix 4*
- A health economic analysis will be performed. The analytic details will be based on the result of the trial and specified (cost-benefit vs cost-minimisation analyses)

The specific elements of the composite outcomes will be reported in supplementary material to the primary publication.

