9.2.2 Timing

Appendix 8 shows an overview of the timing and all variables are defined in *appendix 4*.

Baseline variables (not collected in the screening procedure)

- Sex
- Age at randomisation/date of birth
- Date of admission to hospital and date and time to ICU
- Elective or emergency surgery during current hospitalization (y/n)
- Treatment of suspected or confirmed CDI during current hospital admission (y/n)
- Treatment with NSAID or acetylsalicylic acid at hospital admission (y/n)
- Treatment with anticoagulants at hospital admission (y/n)
- Intravenous thrombolysis within the previous 3 days (y/n)
- Co-morbidities (see definitions in *appendix 4*):
 - history of chronic lung disease
 - history of myocardial ischemia
 - history of severe chronic heart failure (NYHA 3-4)

- history of chronic renal failure in the last year prior to hospital admission
- treatment with at least 0.3 mg/kg/day of prednisolone equivalent for at least one month in the 6 month prior to ICU admission
- active hematologic cancer
- metastatic carcinoma
- AIDS
- Values for simplified acute physiology score (SAPS) II 24 hours prior to randomisation (not covered above): heart rate, systolic blood pressure, core temperature, PaO₂/ FiO₂ ratio, urinary output, urea, white blood cell count, potassium, sodium, bicarbonate, bilirubin, Glasgow Coma Scale (GCS) score (*appendix 9*)
- Variables for severity organ failure assessment (SOFA) scoring 24 hours prior to randomisation not covered in SAPS II scoring: blood platelets, MAP, dose of noradrenalin, adrenalin and dopamine, use of inotropes, plasma creatinine (*appendix 10*)

Daily during ICU admission:

- Delivery of trial medication (y/n)
- Open label treatment with PPI/H₂RA (y/n)
- Invasive or non-invasive mechanical ventilation (y/n)
- Circulatory support (infusion of vasopressor/inotropes) (y/n)
- Any form of renal replacement therapy (y/n)
- Onset of pneumonia (as defined in *appendix 4*) on this day (y/n)
- Treatment with antibiotics (enteral vancomycin, intravenous or enteral metronidazole, or enteral fidaxomicin) for suspected or proven CDI on this day (y/n)
- Acute myocardial ischemia (as defined in *appendix 4*) on this day (y/n)
- Enteral feeding on this day (y/n)
- Number of units of RBCs
- Overt bleeding episodes (hematemesis, coffee ground emesis, melena, hematochezia or bloody nasogastric aspirate) (y/n)
- SARs (y/n) (*appendix 4*)

Bleeding form (only for patients with overt bleeding)

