- Proportion of patients with one or more of the following adverse events: clinically important gastrointestinal (GI) bleeding, pneumonia, *clostridium difficile* infection (CDI), and acute myocardial ischemia
- Proportion of patients with clinically important GI bleeding
- 1 year mortality post-randomisation
- The occurrence of SARs in the ICU

The DMSC will be provided with these data from the coordinating centre as:

Number of patients randomised

Number of patients randomised per intervention group

Number of patients stratified pr. stratification variable per intervention group

Number of events, according to the outcomes, in the two groups

Based on evaluations of these outcomes, the DMSC will decide if they want further data from the coordinating centre and when to perform the next analysis of the data.

For analyses, the data will be provided in one file as described below.

DMSC should yearly be informed about SARs occurring in the two groups of the trial.

The DMSC may also be asked to ensure that procedures are properly implemented to adjust trial sample size or duration of follow-up to restore power, if protocol specified event rates are inaccurate. If so, the algorithm for doing this should be clearly specified.

Conditions for transfer of data from the Coordinating Centre to the DMSC

The DMSC will be provided with a file containing the data defined as follows:

Row 1 contains the names of the variables (to be defined below).

Row 2 to N (where N-1 is the number of patients having entered the trial) each contains the data of one patient.

Column 1 to p (where p is the number of variables to be defined below) each contains in row 1 the name of a variable and in the next N rows the values of this variable.

The values of the following variables should be included in the database:

15. screening_id: a number that uniquely identifies the patient

16. rand_code: The randomisation code (group 0 or 1). The DMSC is not to be informed on what intervention the groups received

17. clin_imp_bleed: clinically important GI bleeding (1 if the patient had one or more episodes and 0 if the patient did not)

18. pneumonia: onset of pneumonia in the ICU after randomisation (1 = one or more episodes, 0= no episodes)

19. clostridium: *clostridium difficile* infection (1 = one or more episodes, 0= no episodes)

20. ami: acute myocardial ischemia in the ICU (1 = one or more episodes, 0= no episodes)

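### As worded in the visible text, the CDI outcome can count a treatment course already running at randomisation; the likely effect is a small dilution of the CDI comparison

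*Combined protocol and SAP*

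**What the plan says.** **Outcome definition.** Protocol Appendix 4, under the definitions of outcome measures, gives "CDI: Treatment with antibiotics (enteral vancomycin, intravenous or enteral metronidazole, enteral fidaxomicin) for suspected or proven CDI". There is no start or onset condition.

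**Data capture.** Protocol section 9.2.2 collects, on each ICU day, whether the listed antibiotics were given "for suspected or proven CDI on this day (y/n"). The SAP's list of daily variables has the same item. In both lists the pneumonia item asks for onset on that day.

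**The other components.** Appendix 4 has "Pneumonia: episodes of newly confirmed pneumonia according to the modified CDC criteria". Acute myocardial ischaemia needs a diagnosis and "receiving treatment as a consequence of this (reperfusion strategies (PCI/thrombolysis) or initiation/increased antithrombotic treatment"). Clinically important bleeding needs overt bleeding plus a fall, a start, an increase or a transfusion within 24 hours.

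**DMSC data file (Appendix 3, unchanged in Appendix 3.1).** One variable is "pneumonia: onset of pneumonia in the ICU after randomisation (1 = one or more episodes, 0= no episodes"); the CDI variable is "clostridium: *clostridium difficile* infection (1 = one or more episodes, 0= no episodes").

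**Patients already treated.** CDI is not among the exclusion criteria in section 4.2. Section 9.2.2 collects at baseline "Treatment of suspected or confirmed CDI during current hospital admission (y/n"). No visible outcome rule, adjustment model, imputation model or sensitivity analysis uses that item.

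**Where CDI enters.** It is part of the four-component composite and of "Proportion of patients with one or more infectious adverse events (pneumonia or CDI) in the ICU" (section 7.2). CDI alone is reported only as a component, in supplementary material.

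**The concern.** A course begun before randomisation cannot have been caused by the trial drug. If it is scored as an outcome, the CDI comparison carries events on which treatment can have had no effect. CDI is one of the harms that motivate the trial (section 1.4), so dilution matters mainly because it could make a real increase look smaller.

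CDI is also the one component for which treatment that is merely continuing is enough. The others, as defined in Appendix 4, need something new or changed. The protocol foresees patients treated for CDI earlier in the admission, since it records them at baseline, but it does not say how a running course on the first trial day is to be scored.

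**Working it through.** **Inputs.** From protocol sections 11.1.2, 11.2.2 and 3.2: 3350 patients allocated 1:1 (n = 1675 per arm), CDI 10% v 8%, two-sided α = 0.05, stated power 53%. The share *q* of patients on a CDI course at randomisation is not in the documents; 0.1% to 2% is assumed.

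**Step 1: reproduce the plan's figure.** With pooled variance under the null, power = Φ[(|p₁ − p₂| − 1.96·SE₀)/SE₁], where p̄ is the mean of the two rates, SE₀ = √(2p̄(1 − p̄)/n) and SE₁ = √([p₁(1 − p₁) + p₂(1 − p₂)]/n).

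For 10% v 8%: SE₀ = √(2 × 0.09 × 0.91/1675) = 0.00989 and SE₁ = √((0.09 + 0.0736)/1675) = 0.00988. Power = Φ(0.0625) = 52.5%, which agrees with the stated 53%.

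**Step 2: add running courses.** If a share *q* of each arm scores as an event because of a running course, the observed rate is q + (1 − q)p. The absolute difference shrinks only by the factor (1 − q). Carried-over cases number 2 × 1675 × q.

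| q (assumed) | Observed rates | RR | Difference (points) | NNT | Power | Carried-over / counted cases |
|---|---|---|---|---|---|---|
| 0 | 10.00% v 8.00% | 0.800 | 2.000 | 50.0 | 52.5% | 0 / 302 |
| 0.1% | 10.09% v 8.09% | 0.802 | 1.998 | 50.05 | 52.0% | 3 / 305 (1%) |
| 0.2% | 10.18% v 8.18% | 0.804 | 1.996 | 50.1 | 51.6% | 7 / 308 (2%) |
| 0.5% | 10.45% v 8.46% | 0.810 | 1.990 | 50.3 | 50.3% | 17 / 317 (5%) |
| 1% | 10.90% v 8.92% | 0.818 | 1.980 | 50.5 | 48.3% | 34 / 332 (10%) |
| 2% | 11.80% v 9.84% | 0.834 | 1.960 | 51.0 | 44.7% | 67 / 362 (18%) |

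The same holds if pantoprazole is the arm with more CDI: at q = 2% a true RR of 10/8 = 1.25 is observed as 11.80/9.84 = 1.20.

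**Step 3: the two outcomes that contain CDI.** Components are taken as independent, for illustration, at the section 11.1.2 rates.

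- Infection outcome: 1 − 0.80 × 0.90 = 28.0% v 1 − 0.84 × 0.92 = 22.7%. Power is 94.0% at q = 0, 93.1% at q = 1% and 92.2% at q = 2%, a loss of at most 1.8 points.
- Composite, adding bleeding 3% v 2% and ischaemia 5% v 4%: power is 97.9% at q = 0, 97.6% at q = 1% and 97.2% at q = 2%, a loss of at most 0.7 points.

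**Step 4: how far this depends on the planning rates.**

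- If new CDI is rarer, say 2% v 1.6% (assumed), q = 1% moves RR from 0.80 to 0.87 and power from 13.8% to 10.3%. Relative dilution is therefore larger, although such a comparison has little power in any case.
- If the planning 10% already contains running courses at q = 1%, the rate of new CDI is (0.10 − 0.01)/0.99 = 9.09%. Power is then 44.1% with running courses counted and 48.0% with those patients left out.

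**Step 5: between-arm bias.** With no treatment effect, both arms have rate q + (1 − q)p, so the null stays true and the type I error is not inflated.

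**The case against.** **The governing definition is not visible.** The SAP states that it governs the primary publication and places the event definitions in its appendix 1, which is not in the text available here. A reader might infer that the final analysis certainly counts running courses. The documents do not support that: the appendix may hold an onset rule, and its absence from this copy is not an omission from the plan. What stands is that protocol Appendix 4, the daily item and the DMSC file show no such rule.

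**Other wording leans towards new events.** The components are called adverse events, which section 8.1 defines as occurring during a trial. Appendix 4 and the SAP count episodes. A line among the daily variables in Appendix 4 lists onset of pneumonia, CDI and ischaemia in the ICU, where onset could be read as covering all three. This shows probable intent. It does not tell a data manager how to score a yes on the first day for a course started on the ward, and both daily forms attach onset to pneumonia alone.

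**The contrast with the other components has limits.** In the DMSC file, bleeding and ischaemia also lack the words after randomisation, and an infarction treated just before randomisation raises a similar boundary question. The difference is that their Appendix 4 definitions need an acute event or a change in treatment, so continuing treatment alone does not qualify.

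**The size is assumed and small.** This is accepted. The 18% of counted cases follows only from the 2% ceiling, and section 1.6.2 already concedes low power for individual side effects.

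**Conclusion.** The point holds as a gap in the visible wording: read literally, a CDI course running at randomisation is an outcome event. It is a minor, optional correction, held with medium confidence because SAP appendix 1 could not be read.

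A reader might infer bias in favour of one arm. Randomisation rules that out in expectation. The effect is neutral between arms and directed towards the null, so it could slightly mask a harm but could not create one.

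For an assumed 0.1% to 2% on treatment at randomisation and the planning rates of 10% v 8%, CDI power drops by between 0.5 and 7.8 points, RR moves from 0.80 to at most 0.83, and NNT from 50 to about 51. The two outcomes containing CDI barely change and 90-day mortality is not affected. The CDI loss is described as small on the strength of the assumed share and the 10% planning rate; with rarer new CDI the relative dilution is greater.

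**What to change.** 1. In protocol Appendix 4 and the DMSC clostridium variable, count a CDI event only when CDI treatment started after randomisation. Put the same sentence in the SAP unless its appendix 1 already says so; in that case align the other two with it.
2. Apply the rule to the CDI component, the infection outcome and the composite, keeping all intention-to-treat patients in the denominator.
3. Look up the treatment start date in the chart only for patients recorded as yes at baseline and yes on the first daily form.
4. Add a sensitivity analysis of the three outcomes that excludes patients with the baseline CDI item recorded as yes. It uses data already collected and covers cases whose start date cannot be found.

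**Cost.** One sentence per definition, one extra analysis, and chart checks for roughly 3 to 67 patients (3350 × 0.1% to 3350 × 2%), because no CDI start date is among the listed variables. Slightly fewer events are counted. The baseline item covers the whole admission, so the sensitivity analysis also drops patients whose earlier course had finished, including any who later had a new episode. Some misclassification remains because the daily data cover ICU days only.
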